## 8.14.6. Dietary Biomarkers

An aliquot of 230  $\mu$ L of plasma will be used for biomarker assays.

## 8.14.6.1. Background

The goals of the dietary collection component of TEDDY are 1) to identify dietary factors that predispose to or protect from islet autoimmunity and T1DM; and 2) to identify potential differences in dietary determinants of islet autoimmunity and T1DM across diverse populations and ethnic groups. TEDDY is designed to test and confirm existing dietary hypotheses as well as explore new, less well-documented hypotheses. Examples of the former include: initiation of persistent islet autoimmunity is associated with 1) early and late exposure to cereals or gluten in the infant diet and/or short duration of breast-feeding; 2) exposure to cow milk in infancy and later in childhood; and 3) lower intake of vitamin D or omega-3 fatty acids, an example of the latter is the collection of maternal diet during pregnancy. Studies from DAISY and BABYDIAB investigators recently suggested a strong association between timing of first exposure to cereals and risk of islet autoimmunity ([name] et al, 2003; [name] et al, 2003). These two studies, while remarkably consistent, did not agree on whether the exposure in question was to all cereals or to only gluten-containing cereals; and whether late first exposure (after 6 months) increased risk of islet autoimmunity in addition to early exposure. In order to investigate this issue further and resolve these discrepancies across studies, it is necessary to use common data collection protocols, the same recruitment criteria and the same follow-up protocols. Questions remain as to whether this association is driven by dose or quantity of exposure, or whether it is related to a proportional measure, such as percent energy from carbohydrates. In order to quantify exposure, one needs to collect information on the entire diet, which would allow one to get absolute intake (as opposed to frequency) and to adjust for energy intake. This requires the collection of a food record. There are no adequate biomarkers to measure the intake of cereals or specifically gluten. The findings of both case-control and cohort studies are inconsistent regarding the putative effects of cow milk intake on beta-cell autoimmunity and type 1 diabetes (reviewed in Virtanen and Knip 2003).

One prospective cohort study and a retrospective case-control study have reported a reduced risk of type 1 diabetes after vitamin D supplementation in infancy (Hypponen et al 2001, EURODIAB 1999). A case-control study suggested that cases of diabetes were less likely to have been given cod liver oil, which contains, in addition to vitamin D, vitamin A and the omega-3 fatty acids, DHA and EPA, in infancy compared with controls (Stene et al 2003). The next step in investigating the role of vitamin D ([name] et al, 2001) and fish oil is to use a prospective study design with complete dietary assessment and biomarkers. Therefore, in addition to the previously mentioned diet records, TEDDY will measure the biomarkers, 25,hydroxyvitamin D and erythrocyte membrane fatty acid composition in blood samples drawn from study subjects.

TEDDY also proposes to study more exploratory hypotheses. In a nested case-control study higher serum alpha-tocopherol levels were related to lower risk of type 1 diabetes in adults (Knekt et al. 1999). Serum alpha-tocopherol is a measure of anti-oxidant status in individuals. We hypothesize that low levels of alpha-tocopherol is associated with the development of islet autoimmunity. Other anti-oxidants, such as the carotenoids, ascorbic acid and selenium could work independently or in concert with alpha-tocopherol in preventing or reversing islet autoimmunity. Therefore, in order to investigate these exploratory hypotheses, we will collect intake of these micronutrients via the diet records as well as measure plasma levels of alpha-tocopherol, the carotenoids, and ascorbic acid. We will measure the anti-oxidant, selenium, via toe nail clippings in order to preserve the blood samples for other biomarkers that can only be measured in the blood.

Haglund et al (1996), Zhao et al (2001) and Stene et al (2002) suggested that zinc concentration in water was inversely associated with diabetes risk. Kostraba et al (1992) and Parslow et al (1997) suggested that higher nitrate concentrations in the water were associated with diabetes risk. Stene et al (2002) suggested that a lower pH level of drinking water is associated with increased diabetes risk. We will investigate these hypotheses in TEDDY by collecting a sample of tap water, which will be tested for zinc, pH and nitrate.

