## 10.1. Master Plan of Analysis

The primary goal of the statistical analyses to be performed as part of this study will be the identification of factors associated with the development of autoimmunity and T1DM. In order to accomplish this, we will employ two different types of analysis, depending on the nature of the factor being studied.

- For those factors whose values will be known to us without additional costs, we will perform log rank tests and Cox Proportional Hazards Regressions. For these analyses, the dependent variable will be the age at which the event being studied (development of autoimmunity or diagnosis of T1DM) occurred. Those not achieving the event when the analyses are being performed and those lost to follow-up without achieving the event will be considered censored as of the date last known to be event-free. The log rank test will be used to study factors with a few discrete values. For example:
  - (a) Family History
  - (b) Haplotype
  - (c) Breast-feeding

For factors with continuous values, we will test for conformity of those values with the proportional hazards assumption by examining the significance of the interaction of the time variable (treated as a time-dependent covariate) with the factor. If there is an indication of a non-zero interaction coefficient, (p < 0.10) we will dichotomize the variable and use the log rank test instead of proportional hazards regression. Otherwise, we will use proportional hazards regression to test for significance at the .01 significance level. The following are examples of factors to be studied in this manner:

- (a) Amounts of certain nutrients consumed
- (b) Duration of breast feeding
- (c) Maternal anxiety and depression as measured by the State Trait Anxiety Inventory and the Edinburgh Postnatal Depression Scale

Proportional hazards regression will be used in both a univariate and multivariate manner and reported both ways. For each factor studied, estimated hazard ratios and their 95% confidence intervals will be computed. When a set of factors that predict conversion to T1DM or autoimmunity are determined as described above, we will compute estimated "survival" curves for subjects having specific factor profiles.

2) For those factors whose determination is costly we will employ a nested casecontrol design. At the time at which a cohort subject converts to autoimmunity or

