The following is a non-exhaustive listing of planned statistical analyses for the prospective part of the project:

- 1. We will classify infants as to whether or not they had early exposure to cereals or gluten in the diet (vs. those receiving only breast milk for the first 3 months). Those exposed will be compared to those not exposed using the Log Rank Test.
- Subjects will be classified, based on diet questionnaires, as consuming low or high levels of anti-oxidants such as carotenoids, ascorbic acid, and selenium. Those with low levels will be compared to those with high levels with respect to the development of T1DM and autoimmunity using Log Rank Tests.

- 3. Subjects' drinking water will be analyzed and subjects classified as drinking water with high or low concentrations of zinc, and nitrate and as low or high pH. Groups will be compared using the Log Rank Test.
- 4. Cox Regression will be used to study the association of the level of psychosocial stress with the development of T1DM and autoimmunity.

The following analyses will be performed in the nested case control portion of the study:

- The association between the number of enterovirus infections a child has and the development of T1DM and islet autoimmunity will be studied with Cox Regression. Using zero as the reference, dummy variables will be created to represent 1, 2, etc infections. The hazard ratios of these values relative to zero will be estimated and p values of the estimates computed. The same type of analyses will be done for the number of rotavirus infections.
- 2. Low levels of omega-3 fatty acids, EPA, and DHA in children's erythrocyte membranes have been associated with increased risk of islet autoimmunity. The odds ratio for each of these exposures will be estimated.
- 3. Low levels of alpha-tocopherol has been associated with increased risk of islet autoimmunity. The odds ratio for each of this exposure will be estimated

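### The low/high log-rank test of antioxidant intake states no energy adjustment and departs from the protocol's own Cox rule for nutrient amounts

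*Protocol*

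**What the plan says.** Section 8.14.6.1 (Background to dietary biomarkers) asks whether the cereal association follows dose or "whether it is related to a proportional measure, such as percent energy from carbohydrates". It concludes that information on the entire diet is needed, "which would allow one to get absolute intake (as opposed to frequency) and to adjust for energy intake". The same section takes intake of carotenoids, ascorbic acid and selenium from the diet records. Energy intake is itself a factor of interest: Table 4 lists it, and section 8.12.1.2 names it among the changes to be included when T1D risk is assessed in the peripubertal years.

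Section 10.1 handles nutrient intake in two ways.

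- **General rule for continuous factors.** "Amounts of certain nutrients consumed" is the first example of a factor for Cox regression. "Proportional hazards regression will be used in both a univariate and multivariate manner and reported both ways". Only if the time interaction has p < 0.10 does the rule change: "we will dichotomize the variable and use the log rank test instead of proportional hazards regression".
- **Item 2 of the prospective list.** "Subjects will be classified, based on diet questionnaires, as consuming low or high levels of anti-oxidants such as carotenoids, ascorbic acid, and selenium". A log-rank test then sets the two groups against each other for both endpoints. No cut-point, energy basis, covariate or stratum is given.

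No analysis in section 10 mentions energy.

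**The concern.** A child who eats more of everything tends to take in more of each nutrient. A split on absolute intake therefore tends to separate big eaters from small eaters as well as high from low antioxidant consumers, and a log-rank test without strata cannot tell the two apart. If energy intake bears on risk, the comparison picks up part of that relation.

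The direction matters for the study's hypothesis. Section 5 (item 1c) expects lower antioxidant intake to raise risk. If eating more raises risk, the distortion runs the other way: it could hide a protective effect or make high intake look harmful.

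The general rule in section 10.1 offers some protection through multivariate Cox regression, but item 2 names a different test for these nutrients. When the proportional hazards check fails, the rule moves to a log-rank test as well, and the regression route to adjustment is lost for that nutrient.

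**Working it through.** **Inputs from the protocol.** Two-sided alpha 0.01 (section 10.3). Cases of T1DM by age 15: 281 general population + 105 relatives = 386 (section 10.3, summary after Table 5). About 460 pooled cases in the scenario of section 10.5.3. Table 6: N = 7013, 4% of unexposed by 15 years.

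**Assumed inputs, because the protocol gives none.** Correlation r between nutrient and total energy: 0.3 to 0.7. Hazard ratio h per SD of energy: 1.0 to 1.5. The nutrient has no effect of its own and is split at the median.

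**1. The plan's own figure.** Table 6 states power 0.81 at HR 1.5, 20% exposed, no losses. Lakatos' method with exponential hazards, 5 years of uniform accrual and the 15 years of post-accrual follow-up stated in section 10.3 gives 0.80. At 1, 5 and 10% exposed it gives 0.05, 0.26 and 0.52, as stated. Table 8 gives 0.95 at the same setting, also as stated. The tabulated power is thus that of an unadjusted two-group test.

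**2. Size of the possible bias.** For a median split of a normally distributed nutrient, mean energy differs between the groups by 2r√(2/π) = 1.596r SD. Then:

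- spurious HR = exp(1.596 · r · ln h)
- drift z = ln(spurious HR) · √(D/4), with D events
- rejection = Φ(z − 2.576) + Φ(−z − 2.576)

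At r = 0.5, h = 1.3 and D = 386: ln HR = 1.596 × 0.5 × 0.2624 = 0.209, so HR = 1.233. Then z = 0.209 × √96.5 = 2.06, and rejection is 0.302.

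| r | h | spurious HR | rejection, D = 386 | rejection, D = 460 |
|---|---|---|---|---|
| any | 1.0 | 1.00 | 1.0% | 1.0% |
| 0.3 | 1.1 | 1.05 | 1.8% | 2.0% |
| 0.5 | 1.2 | 1.16 | 12.6% | 15.5% |
| 0.5 | 1.3 | 1.23 | 30% | 37% |
| 0.7 | 1.3 | 1.34 | 62% | 71.5% |
| 0.7 | 1.5 | 1.57 | 97% | 99% |

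At r = 0.5 and h = 1.3, a true HR of 0.80 for high intake would show as about 0.80 × 1.233 = 0.99.

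**3. Price of adjustment.** With energy in the model, and assumed measured without error, the spurious HR returns to 1.00 and rejection to 1%. For a top-20% group, the correlation of group membership with energy is r × 0.280/√(0.2 × 0.8) = 0.70r, so the information kept is 1 − (0.70r)². The unadjusted drift in Table 6 (HR 1.5, 20% exposed) is 3.43. At r = 0.5 it becomes 3.43 × √0.878 = 3.21, and power is Φ(3.21 − 2.576) = 0.74. At r = 0.3 / 0.5 / 0.7:

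- Table 6 falls from 0.80 to about 0.78 / 0.74 / 0.66.
- Table 8 falls from 0.95 to about 0.94 / 0.92 / 0.87.

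**The case against.** The strongest reply is that adjusted analysis is already planned. Section 10.1 reports Cox regression multivariately as well as univariately, section 10.6 plans multivariate models with time-dependent covariates, and item 2 stands in a list introduced so: "The following is a non-exhaustive listing of planned statistical analyses for the prospective part of the project". The choice of covariates is ordinary content of a statistical analysis plan, which is not at hand. This stands against any claim that adjustment is absent from the plan. It does not change what item 2 names as the test, or the departure from the general rule.

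A reader might infer that the protocol commits to unadjusted intake and that food quantity will therefore be read as a nutrient effect. The text does not support this. Item 2 neither states nor excludes an energy-adjusted split, and the bias is zero if energy is unrelated to outcome. Nor does item 2 reverse a commitment: the energy sentence in section 8.14.6.1 arises from a question about cereals and describes what food records make possible.

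A reader might also infer that item 2 swaps food records for a cruder questionnaire. Table 2 lists the 3-day diet record under its diet questionnaires, so the wording can include the records.

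Nor does the protocol say that total energy raises risk. Section 8.11 hypothesises a pattern of high caloric intake in a single meal, and section 5 (item 1h) hypothesises excessive weight gain. Both are neighbouring ideas, not a stated effect of total intake.

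Finally, plasma carotenoids and ascorbic acid and toenail selenium give other evidence on antioxidants. They do not correct the intake test.

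**Conclusion.** The point holds as a mismatch in wording with a possible bias behind it. Item 2 fixes a two-group log-rank test on antioxidant intake with no stated covariate, stratum or energy basis. It leaves unused the energy adjustment that section 8.14.6.1 gives as one reason for food records, and it dichotomizes from the start where the general rule does so only after a failed proportional hazards check.

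The comparison may mix total food intake with a nutrient effect, provided that energy intake is related to risk. The spurious HR of 1.00 to about 1.57 and the rejection of 1% to about 97% (386 events) rest wholly on the assumed r and h, on a median split and on absolute intake being used. They show how the problem scales and do not estimate its size in this cohort. This is a cheap improvement of low severity.

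**What to change.** Reconcile the general rule and item 2 in section 10.1 so that the main nutrient-intake result takes one of two forms:

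- a Cox model with the nutrient and total energy from the same 3-day records; or
- where a low/high split or a log-rank test is used, including the fallback after a failed proportional hazards check, a split on energy-adjusted intake (for example the residual on total energy, or the amount per unit of energy) within age and country.

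Show the result for unadjusted intake beside it.

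The cost is wording, a little analysis work and the loss of power shown in the working. No new data are needed, because energy intake is already among the nutritional factors in Table 4. Error in recorded energy would leave some confounding in place, so the adjusted result is better but not exact.

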## 8.14.6.2. 25, hydroxyvitamin D

25, hydroxyvitamin D will be assayed using 50  $\mu$ L of plasma collected from the infant at the age of 3 months, 6 months, 9 months and 12 months, and annually thereafter. The assay is an ELISA.

## 8.14.6.3. Alpha tocopherol, gamma tocopherol

Alpha tocopherol, and gamma tocopherol will be assayed using 70  $\mu$ L of plasma collected from the infant at 6 months of age, 12 months and annually thereafter. The collection tubes should be amber or foil-covered in order to avoid exposing the sample to light. The plasma should be separated immediately and the plasma sample should be frozen at  $-70^{\circ}$ C. Alpha- and gamma-tocopherol will be measured by HPLC. Total lipids will be measured using a colorimetric assay (Knight et al., 1972).

# 8.14.6.4. Carotenoids (beta-carotene, alpha-carotene, lycopene) and Ascorbic Acid

Carotenoids and ascorbic acid will be measured in plasma on samples taken at 6 months, 12 months and then annually. The blood sample should be kept from light using foil covered blood collection tubes and amber storage tubes. For the ascorbic acid assay, the plasma will be put in trichloride acetic acid for

storage. The assays will be HPLC. The carotenoid assays require 60  $\mu$ L of plasma, and the ascorbic acid assay requires 50 $\mu$ L of plasma.

A paired-ion, reversed-phase, high-performance liquid chromatography procedure using electrochemical detection and internal standard quantitation with isoascorbic acid is used for the determination of ascorbic acid.

## 8.14.7. Erythrocyte Membrane Fatty Acid

Erythrocyte membrane fatty acids will be assays using 500  $\mu$ L of red blood cells. The samples of red blood cells will be initially extracted for lipids. A neutralpolar separation utilizing a dry column, based on the method of Marmer and Maxwell (Marmer and Maxwell, 1981) will be performed. The fatty acids present will be methylated using the base-catalyzed procedures in preparation for analysis by gas chromatography with mass spectral detection.

## 8.15. Whole Genome Sequencing and Epigenetics Studies

To fully examine the genetic basis of islet autoimmunity in the TEDDY study, a comprehensive determination of genomic variation, through whole genome sequencing (WGS) will be conducted. TEDDY also plans to characterize the occurrence and potential functions of epigenetic modifications, using both global, unbiased approaches as well as the study of smaller chromosomal regions when appropriate, in order to understand how epigenetic regulatory mechanisms contribute to beta cell autoimmunity and T1D. Deep whole genome sequencing and epigenetic analyses will be completed on DNA samples from TEDDY subjects positive for islet autoantibodies or who have progressed to the clinical onset of diabetes and matched autoantibody negative TEDDY control subjects.

DNA samples from TEDDY parents will be used for estimating Mendelian inheritance errors (as one of the quality control criteria from the whole genome sequencing data set). By including the parents' samples, we will be able to compare the genotypes of the children to the parents; hence we will be able to provide estimation of Mendelian inheritance error rates. Moreover, whole genome sequences of a family of four, consisting of two siblings and their parents, will allow us to delineate recombination sites precisely and identify very rare single nucleotide variants.

DNA samples will be received at the University of Virginia for initial processing and quality control, followed by receipt at Macrogen USA for whole genome sequencing. DNA samples for epigenetic analyses will be sent to a TBD laboratory.

Whole genome sequencing data that are to be made available with specific datasharing restrictions (consent) will need to be registered with the appropriate

[figure not shown]
consent/data sharing information at the dbGaP, through the dbGaP Registration Portal/System. Access to those sequence data will be only through the dbGaP, according to the data sharing specification signed by participants.

## 8.16. Parental and sibling DNA collection

The HLA region encompasses many hundreds of genes that are more or less in complete linkage disequilibrium within extended haplotypes. In TEDDY we designate major immune response gene haplotypes by their DRB1-DQA1-DQB1 allele associations, but they are in fact much more extensive. Even for DR and DQ our definitions of haplotypes with only typing of the TEDDY child is probabilistic for the haplotypic association (alleles of these different genes on the same chromosome). In some cases, even probabilistic definition is not possible (e.g. specific DRB1\*04 alleles with individual having two DR4 haplotypes with alleles DQB1\*0301 and DQB1\*0302 it is not possible to assign which DR4 allele (e.g. 0401 or 0404) goes with which DQ allele). In addition, for families in which there is an affected sibling, without genetic analysis of that sibling, we have no information as to inheritance of haplotypes identical by descent (IBD) for the TEDDY child. For families in which one child is DR3/4 and has diabetes and the sibling followed in TEDDY is also DR3/4, there is only an approximate 2/3 chance that the DR3/4 haplotypes (one haplotype from mother and one from father) were inherited identical by descent. This lack of identity by descent occurs for instance when one parent is homozygous for DR3 and passes on a different DR3-containing chromosome to each child. Though HLA haplotypes are emphasized here, the same general concepts apply to haplotype definition anywhere in the genome.

There is substantial evidence in the literature that inherited haplotypes that are identical by descent with an affected family member can confer very high risk of T1D to other family members. Analysis of siblings of patients with T1D (with parents) from the DAISY study has been particularly interesting as it was possible to define inheritance of both HLA regions identical by descent with their proband. For DR3/4-DQ2/DQ8 sibling identical by descent for the HLA, a risk of activating islet autoimmunity by age 12 as high as 80% was observed (Figure 2).

Figure 2

In order to discover additional genes within those extended haplotypes that contribute to T1D development in the child, one must determine which extended haplotypes were (and were not) passed to ultimately affected children. The most practical way to do this is to collect genomic DNA from each parent and sibling of each TEDDY child via one 5 ml venous blood sample. The parents and sibling must each undergo standard informed consent and sign a consent/assent form prior to sample collection. Collection can occur via TEDDY phlebotomists at the Clinical Centers at the same visit where blood is collected on the TEDDY child. Each center will obtain local IRB approval for sampling these additional subjects as part of TEDDY.

Genotyping of these samples is planned using a nested case-control design similar to that approved for other analyses of reposited TEDDY samples. This will not occur for a number of years until the endpoint status of the subjects (islet antibodies and/or diabetes) is known. The extensive genotyping required will likely be available in a more complete fashion at lower cost at that time. Samples chosen for genotyping will be analyzed at a large number of polymorphisms (e.g. SNPs, microsatellites or specific alleleic probes) across a wide area of the human HLA region and potentially other regions as the architecture of the genome is better defined. Analyses will then determine which inherited extended haplotypes appeared to confer elevated T1D risk and which did not.

While there are many possible genetic variations among the extended haplotypes, it is clear that this large TEDDY study will have sufficient samples to identify

features in common to either high-risk or low-risk extended HLA haplotypes. Such information is likely to contribute to analysis of gene-environment interactions affecting the development of T1D in the affected TEDDY children. A very simple first analysis would be to analyze families with a DR3/4 "high risk" TEDDY child who has an affected sibling, for analysis of development of anti-islet autoantibodies and T1D stratifying the TEDDY children by whether they inherit both HLA haplotypes identical by descent (versus not) to their proband sibling. It would take less than 82 siblings by simple proportions analysis of autoantibody cases (21 per group) to have power of 0.8 (alpha .05), based on autoantibody frequency estimates from the DAISY study. In some cases, interactions of HLA risk with binary environmental factors (yes or no exposure) will be best revealed via analyses of TEDDY children that are not IBD at both haplotypes with an affected first degree relative, but rather are at a somewhat lower genetic risk. In this case the effect of a specific binary environmental factor would presumably be more apparent. On the other hand, if very high risk (e.g. 80% risk by age 12) is confirmed in TEDDY children identity by descent at both haplotypes with an affected relative, this would be an ideal population to evaluate for timed influence of environmental factors on activating autoimmunity. In addition to analysis of identity by descent where the affected sibling is obviously crucial, for the determination of TEDDY participant haplotypes, non-affected siblings are also important. as many families will be non-informative for defining haplotypes of the TEDDY participant unless information on additional siblings is available. This is simply a result of increased informativeness of the family depending on inheritance of different haplotypes among siblings. In summary, we believe this genetic information, only available if DNA is obtained from parents and siblings, will be highly useful in TEDDY analyses.

As noted above, genotyping on these samples will not occur for a number of vears, after the highest-risk period for development of T1D in the siblings is likely to have already passed. Additionally, the greatest risk to the child and family from this type of genetic analysis is the discovery of non-paternity. Therefore, families will not be told the identity of any specific alleles or haplotypes based on genotyping TEDDY parent or sibling samples. This policy is consistent with the longstanding TEDDY policy prohibiting any release of specific allele or haplotype information on the TEDDY child. At the time of consent, families will be informed that genetic typing results will not be available for many years on TEDDY siblings or parents, and that only general T1D HLA risk levels will ever be available. In the future, when those general risk levels are conveyed to the family, the same genetic counseling procedure and features that are used in TEDDY children will be followed. To ensure adherence to the above policy, specific parent and sibling genotyping allele or haplotype information will never be available to TEDDY clinic staff, but only to TEDDY investigators performing genetic or gene-environment analyses on this data. It should be noted that many TEDDY family members (e.g. First Degree Relatives) are eligible for risk marker testing as part of other diabetes studies approved by local IRBs at many of the

Clinical Centers, and centers are encouraged to make this testing available to all eligible TEDDY family members.

